10.7.2. Non-Compliers and Missing Data

Non-compliers will be defined as subjects who meet one of the following:

- subjects who did not receive the full dose of BPL HRIG/comparator HRIG [not eligible for primary PK population];
- subjects who did not receive the first 3 doses of active rabies vaccine at the time specified [not eligible for primary PK population];
- randomized without meeting all eligibility criteria [may be eligible for primary PK population];
- subjects with any major protocol deviations reported [may be eligible for primary PK population].

Specifically, the following two analyses will be performed to assess impact on primary PK analysis:

- The primary PK analysis will be repeated assuming that non-compliant subjects did not attain an RVNA titer of ≥ 0.5 IU/mL at Visit 6. [worst case scenario]
- The primary PK analysis will be repeated assuming that non-compliant subjects successfully attain an RVNA titer of ≥ 0.5 IU/mL at Visit 6. [best case scenario]

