7. GENERAL ANALYSIS CONVENTIONS

All tables, figures and listings will be produced using SAS (v9.4 or a more recent version).

Unless otherwise stated, categorical data will be presented using counts and percentages, whilst continuous variables will be presented using the mean, 95% confidence interval for the mean, standard deviation (SD), median, minimum, maximum, number of subjects (n) and number of missing subjects or data points. Minima and maxima will be quoted to the number of decimal places as recorded in the CRF; means, SDs and medians will be quoted to one further decimal place. Percentages will be rounded to one decimal place.

Subjects who withdraw from the analysis will have their data analyzed to the point of withdrawal. Subjects who complete all required assessments up to and including Day 14 will be eligible for the primary PK population. Other subjects who withdraw from the study will be eligible for the ITT population. Unblinded subjects will continue in study after being unblinded unless noted otherwise.

For the purpose of the statistical analyses visit labels may be used interchangeably as Visit and Day as in the table below regardless of actual timing of study visit. Sensitivity analyses will be performed to address any potential visit timing issues.

Visit Label	Visit 1	Visit 2	Visit 3	Visit 4	Visit 5	Visit 6	Visit 7	Visit 8	Visit 9
Intended Day	Day -28	Baseline, Day 0	Day 3	Day 5	Day 7	Day 14	Day 28	Day 49	Day 140

a. DEFINITION OF STATISTICAL SIGNIFICANCE

- Primary Efficacy Endpoint

The BPL HRIG treatment effect will be considered non-inferior to the active comparator HRIG treatment when the resultant p-value from the one-sided Farrington-Manning

Score Test for proportion difference is [REDACTED].

- Secondary Efficacy Endpoints

The secondary efficacy endpoint analyses will be considered statistically significant using a two-sided significance level of 0.05.

b. ANALYTIC POPULATIONS

The following analysis populations will be defined for this study.

- Intent-to-Treat [ITT] Population

The intent-to-treat (ITT) population will include all randomized subjects. All analyses will be performed using the ITT population.

- Safety Population

The safety population will be defined as all subjects who receive at least one dose of BPL HRIG / comparator HRIG. Safety data will be analyzed up to the point of withdrawal for applicable subjects. The safety population will be used for all safety analyses.

- Per Protocol [PP] Population

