The per protocol population will be split into the **primary** and **secondary** PK populations.

The **primary PK population** will be defined as all subjects who receive the full dose of BPL HRIG / comparator HRIG and the first 3 doses of active rabies vaccine on Visits 2, 3, and 5, and for whom the PK sample at Visit 6 is taken. This population will be used for the primary PK analysis and selected secondary PK analyses. The **secondary PK population** will be defined as all subjects who receive the full dose of BPL HRIG / comparator HRIG and all 5 doses of active rabies vaccine and for whom all required PK samples are taken. This population will be used for selected secondary PK analysis and the exploratory analysis.

Subjects with a pre-dose RVNA of \geq the LLOQ will be excluded from the all

analyses.

[REDACTED]

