[REDACTED] will be performing the RFFIT test and providing the results for data analysis. Subject serum will be tested in duplicates. If either individual test in duplicated set 1 fails QC, a second duplicate set of RFFIT tests will be run. The arithmetic mean value of the appropriate duplicate set, (set 1 if QC passed, set 2 if QC failed), will be used for the final reported rabies antibody titer [IU] for primary endpoint derivation. If the final arithmetic mean value is ≥ 0.5 IU/mL that subject-specific time point will be coded as 1 (success); otherwise if the final arithmetic mean value is < 0.5 IU/ml the time point will be coded as 0 (failure). If both duplicate sets fail the QC test,

the subject data is deemed non-evaluable. The proportion of subjects with RVNA titer ≥ 0.5 IU/mL is calculated as follows:

$$\frac{\sum(\text{successes}, 1)}{\sum(\text{all evaluable subject } i, n)}$$

Sensitivity analyses will be performed to assess impact of missing data, see section 8j.

f. SECONDARY EFFICACY ANALYSES

Secondary efficacy analyses 2 and 5 will be based on the secondary PK population. Secondary efficacy analyses 1, 3, and 4 will be based on the primary PK population, since timepoints post-Visit 6 are not included in these analyses.

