- The number and percentage of subjects reporting AEs, serious AEs, study medication-related AEs, AEs leading to withdrawal and AEs leading to death.
- The number of AEs, serious AEs, study medication-related AEs, AEs leading to withdrawal and AEs leading to death.

SUMMARY OF AEs BY SEVERITY OF EVENT

The number and percentage of subjects reporting AEs, and study medication-related AEs, will be summarized by the system organ class and by the preferred term. The severity of event will be recorded once per subject for each term as the maximum severity experienced by each subject (i.e. where the order of most severe to least severe is given by: severe, moderate and then mild).

SUMMARY OF AEs BY CAUSALITY

The number and percentage of subjects reporting AEs will be summarized by the system organ class and by the preferred term. The causality will be recorded once per subject for each term giving the most likely relationship to study medication (i.e. in the order: very likely/certain, probable, possible, unlikely and then unrelated).

i. SENSITIVITY ANALYSES

Sensitivity analyses will be performed to assess the impact on the primary PK analysis of non-compliers within the ITT population, missing primary endpoints, and timing of vaccine dosing.

POTENTIAL INTERACTION

Before treatment unblinding, timing of vaccine dosing and PK sampling, if not performed on the designated day, will be assessed as potential effect modifiers on the association between RVNA levels and treatment group in the primary and secondary PK analysis. A chi-square or fisher's exact test, as appropriate, will be used to measure the association between the dichotomous indicator of receiving dose/PK sampling on the intended day

[yes/no] and target level of RVNA titer reached [yes/no]. If the association is significant at the 0.05 level, a subgroup analysis including only subjects who were dosed/sampled on the target day will be reported in addition to the full analysis.

NON-COMPLIERS AND MISSING DATA

Non-compliers will be defined as subjects who meet one of the following:

- subjects who did not receive the full dose of BPL HRIG/comparator HRIG [not eligible for primary PK population];
- all 3 doses of active rabies vaccine at the time specified [not eligible for primary PK population];
- randomized without meeting all eligibility criteria [REDACTED];
- subjects with any major protocol deviations reported [REDACTED].

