Specifically, the following two analyses will be performed to assess impact on primary PK analysis:

- The primary PK analysis will be repeated assuming that non-compliant subjects did not attain an RVNA titer of ≥ 0.5 IU/mL at Visit 6. [worst case scenario]
- The primary PK analysis will be repeated assuming that non-compliant subjects successfully attain an RVNA titer of ≥ 0.5 IU/mL at Visit 6. [best case scenario]

j. SUBGROUP ANALYSES

Subgroup analyses will be performed as appropriate, due to either imbalance randomization in baseline subject demographics and/or clinical relevance to primary and secondary PK analyses and safety analysis. Factors including, but not limited to, age, race, BMI, and sex will be considered. Subgroups will be defined based on population median.

K. MISSING VALUES

No missing value imputation methods will be applied, e.g. the analyses are based on a valid case basis.

I. INJECTION SITE OBSERVATIONS

Injection site observations data will be summarized as appropriate.

SUMMARY BY PRODUCT

The number and percentage of subjects reporting injection site reactions will be summarized by preferred term and product (HRIG or vaccine).

SUMMARY BY NUMBER OF INJECTIONS

The number and percentage of subjects reporting injection site reactions will be summarized by preferred term, product (HRIG or vaccine) and number of injections.

M. VIRAL SEROLOGY VARIABLES

Viral serology variables will be summarized. Shift tables for virology will present the number of subjects with positive and negative results and those for whom the results change during the study.

N. HEMATOLOGY, SERUM BIOCHEMISTRY, URINALYSIS

Hematology, serum biochemistry and urinalysis variables will be summarized, including changes from baseline. Shift tables for hematology and biochemistry variables will be provided for the number and percentage of subjects with values below, within and above the reference range.

O. MARKERS OF HEMOLYSIS

Markers of hemolysis will be summarized, including changes from baseline.

p. VITAL SIGNS AND BODY TEMPERATURE

Sitting diastolic and systolic blood pressure, pulse rate, body temperature and respiration rate will be summarized, including changes from baseline (i.e. pre-dose on Visit 2 for body temperature, Screening for all other parameters). In addition, the number of subjects with “substantial” increases or decreases from baseline in blood pressure (>20 mmHg) and pulse (>15 b.p.m.) will be summarized.

q. PHYSICAL EXAMINATION

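### The runs labelled worst and best case impute the same outcome in both arms, so they do not bound the non-inferiority difference; missing Day 14 titers are not clearly covered

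*SAP*

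**What the plan says.** The primary analysis is per-protocol. It uses the primary PK population, which requires the full HRIG dose, the first three vaccine doses, and is limited to subjects "for whom the PK sample at Visit 6 is taken" (SAP 7b, 8e). The test is of p - p0 against -0.1.

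SAP 8i and protocol 10.7 say the sensitivity analyses will address "non-compliers within the ITT population, missing primary endpoints, and timing of vaccine dosing". Two runs follow. In one, "The primary PK analysis will be repeated assuming that non-compliant subjects did not attain an RVNA titer of" at least 0.5 IU/mL at Visit 6, labelled worst case. In the other they are all assumed to have attained it, labelled best case. Neither run distinguishes the arms.

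Non-compliers are those with an incomplete HRIG dose, "subjects who did not receive the first 3 doses of active rabies vaccine at the time specified", an eligibility failure, or a major protocol deviation (protocol 10.7.2, which shows the list without redaction).

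Three other statements bear on missing titers:
- SAP 8e: if both RFFIT duplicate sets fail QC, "the subject data is deemed non-evaluable".
- SAP 8e: "Sensitivity analyses will be performed to assess impact of missing data, see section 8j". Section 8j is Subgroup Analyses.
- SAP 8k: "No missing value imputation methods will be applied".

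SAP 7b and protocol 10.4 also state "All analyses will be performed using the ITT population".

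**The concern.** There are three linked problems.

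**(a) The labels do not match what the runs do.** Setting everyone to failure gives the lowest possible rate in each arm, and setting everyone to success gives the highest. A difference is at its lowest when the test arm's unknowns fail and the comparator's succeed. With equal losses, both planned runs leave the difference where it was. With unequal losses the labelled worst case can be harsher or more lenient than the complete-case result, depending on which arm lost more.

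**(b) The missing-endpoint group falls through.** A subject who misses one of the first three vaccine doses is a non-complier and is imputed. A subject dosed through Visit 5 with no Visit 6 sample, or with two failed assay sets, leaves the primary analysis and meets no listed criterion, unless the event happens to be called a major deviation.

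**(c) Observed data are overwritten.** A non-complier may well have a valid Day 14 titer. Protocol 10.7.2 allows that those with eligibility failures or major deviations may even be in the primary PK population. Both runs replace those titers with an assumed value.

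The two runs will be read as the limits of a per-protocol non-inferiority result. As defined, they could show robustness that the data do not support.

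**Working it through.** **Inputs.** Protocol 10.9: 98% success in both arms, margin 10%, one-sided 0.025, 85% power, 73 evaluable of 81 per arm, 10% loss. Protocol 10.5.1: Farrington-Manning test. Losses by arm are not given and are assumed below.

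**The plan's own figure.** Under the null, the restricted estimates for p = 0.98 are 0.8895 and 0.9895. Then

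n = [1.960·√(0.8895·0.1105 + 0.9895·0.0105) + 1.036·√(2·0.98·0.02)]² / 0.10² = 72.4,

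so 73 per group, as stated. Also 162 × 0.9 = 145.8, about 146, and 81 - 73 = 8 lost per arm.

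**Method for the limits.** The lower limit is the δ that solves

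(p̂_BPL - p̂_comp - δ) / √[p̃_B(1 - p̃_B)/n_B + p̃_C(1 - p̃_C)/n_C] = 1.96,

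where p̃_B and p̃_C are the maximum-likelihood estimates constrained to differ by δ. With no imputation, 72/73 v 72/73 gives -6.1%.

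**Equal losses.** Take 72/73 observed per arm plus k non-compliers per arm. The labelled worst case compares 72/(73+k) with itself. The true bound compares 72/(73+k) with (72+k)/(73+k).

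| k per arm | Labelled worst case | BPL fail, comparator succeed |
|---|---|---|
| 2 | -7.6% | -9.95% |
| 3 | -8.2% | -11.6% |
| 5 | -9.2% | -14.7% |
| 7 | -9.9% | -17.4% |
| 8 | -10.2% | -18.7% |

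At k = 8 the point difference is 0 in both planned runs. The outcomes compatible with the data run from 72/81 - 80/81 = -9.9% to +9.9%.

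**Range over the observed rate.** With 71/73 observed, the labelled run crosses -10% at k = 6 and the bound at k = 2 (-10.6%). With 73/73, the labelled run is still inside at k = 8 (-9.8%) and the bound crosses at k = 3 (-11.0%).

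**Unequal losses, 81 per arm, labelled worst case.**

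| Lost, BPL v comparator | Observed | Limit, observed | All set to failure | Limit, labelled worst case |
|---|---|---|---|---|
| 5 v 1 | 75/76 v 79/80 | -6.0% | 75/81 v 79/81 | -13.1% |
| 4 v 8 | 76/77 v 72/73 | -5.8% | 76/81 v 72/81 | -4.1% |
| 4 v 12 | 75/77 v 68/69 | -7.7% | 75/81 v 68/81 | -1.35% |

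In the last two rows the worst case looks better for BPL than the observed data.

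**The uncovered group alone.** Against 72/73 in the comparator arm, BPL subjects with no evaluable titer counted as failures give:
- one (72/74): -8.1%
- two (72/75): -9.9%
- three (72/76): -11.6%

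**Tipping-point grid at 8 per arm.** Compare (80 - f_B)/81 with (80 - f_C)/81 for f_B, f_C = 0 to 8 imputed failures. Of the 81 cells, 30 are at or below -10%. The first crossing is 3 BPL v 0 comparator failures (-10.95%), followed by 4 v 1 (-11.5%), 4 v 2 (-10.5%), 5 v 3 (-11.0%) and 6 v 4 (-11.5%).

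**The case against.** - **The plan never calls the runs bounds.** It says they assess impact, and the labels fit the response assumption. That is fair as a reading of intent. But a worst case for a non-inferiority comparison that can improve the test product's result is mislabelled.
- **The opposite-direction corner fails at modest loss whatever the data, and at the planned 8 per arm the labelled run also fails.** Both are true. The corner alone is therefore a poor test of robustness, and the grid is the more useful tool. The disagreement at 3 to 7 per arm remains.
- **The reversal needs 4 v 12 losses in a randomized trial with blinded subjects and investigators.** That imbalance is assumed and is not likely. A milder one, 4 v 8, already moves the limit in BPL's favour.
- **The plan decides on an exact interval, and the limits above are score-based.** This stands for the near-margin cases. An exact unconditional test ordered by the Farrington-Manning statistic gives p = 0.0256 for 72/75 v 74/75 and p = 0.0253 for 72/75 v 72/73, so both fall just outside. That makes the bound slightly harsher and does not change the contrast at 3 to 7 per arm.
- **Reserve samples (protocol 7.9.1) make permanent assay loss less likely, and a missed sample might be a major deviation.** The group is probably small. Still, neither provision assigns an outcome to a missing titer.
- **The ITT sentence, the 8j pointer and the 8k rule can be read sensibly.** These are clarifications, and they would not justify the point by themselves.

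**Conclusion.** The concern holds. The planned runs bound each arm's rate and not the difference. For 72/73 observed per arm, the labelled worst case stays inside -10% from 3 to 7 non-compliers per arm while the true bound does not. The stated aim of assessing missing primary endpoints is not met for subjects who complete dosing through Visit 5 but have no valid Visit 6 titer, and three such subjects in the BPL arm alone could cross the margin.

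These sizes rest on assumed losses by arm, on an observed success rate near the planned 98%, and on score limits. The exact interval named in the plan was not computed. The primary estimate, test and error rate are unaffected. What fails is the robustness check, which should be corrected before unblinding because a tipping analysis chosen afterwards carries less weight.

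**What to change.** 1. State that the ITT analysis repeats the primary comparison in all randomized subjects, apart from the plan's pre-dose RVNA exclusion, using every valid Visit 6 titer, including those of non-compliers.
2. In the missing-data runs, impute only subjects without a valid Visit 6 titer. Name missed samples and double QC failures explicitly.
3. If the two same-direction runs are kept, rename them all failures and all successes. Add BPL fail/comparator succeed as the extreme bound, and a tipping-point grid of imputed failures by arm. Judge robustness on the grid and not on the extreme corner alone.
4. Correct the SAP 8e cross-reference from 8j to 8i, and state that these runs are exempt from the no-imputation rule in 8k.

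The cost is SAP wording and a few lines of code, with no change to design, endpoint or sample size. The drawback is that the reported worst-case limit will look less favourable, and the extreme corner will fail at modest loss whatever the data, so it has to be presented with the grid.

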10.6.1. Adverse Events

Adverse events (AEs) will be reported by the MedDRA system organ class and preferred term. Only treatment-emergent AEs, defined as those events with onset date from dosing with BPL HRIG / vaccine or comparator HRIG / vaccine will be included in the summary tables. All AEs will be included in the data listings.

Treatment-related AEs will be defined as events recorded as having a possible, probable or very likely/certain causality to treatment. AEs leading to withdrawal will be defined as events where the subject's participation in the study was discontinued as a result of the AE.

AEs will be summarized descriptively for all subjects and by treatment group. The denominator used for the calculation of percentages will be the number of subjects in the safety population per treatment group. For all AE summaries described below, counting will be performed by subject and event. For counts by subject, subjects experiencing the same event more than once

will have that event counted only once within each system organ class and once within each preferred term.

The following summaries of treatment-emergent AEs will be provided:

Summary of AEs

- 1) The number and percentage of subjects reporting AEs, serious AEs, study medication related AEs, AEs leading to withdrawal and AEs leading to death.
- 2) The number of AEs, serious AEs, study medication-related AEs, AEs leading to withdrawal and AEs leading to death.

Summary of AEs by Severity of Event

The number and percentage of subjects reporting AEs, and study medication-related AEs, will be summarized by the system organ class and by the preferred term. The severity of event will be recorded once per subject for each term as the maximum severity experienced by each subject (i.e. where the order of most severe to least severe is given by: severe, moderate and then mild).

Summary of AEs by Causality

The number and percentage of subjects reporting AEs will be summarized by the system organ class and by the preferred term. The causality will be recorded once per subject for each term giving the most likely relationship to study medication (i.e. in the order: very likely/certain, probable, possible, unlikely and then unrelated).

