5. REPORTING SERIOUS ADVERSE EVENTS

When an Adverse Event occurs, which fulfils the definition of serious (see Section 2.6 for definition) the Investigator must complete and sign the serious adverse event form and send it within 24 hours to the appropriate contact.,

Medical cover for urgent queries relating to adverse events will be provided on 24 hours / 7 days a week by the following:

[REDACTED]

All SAE reports must be e-mailed or faxed directly to [REDACTED] at [REDACTED] or [REDACTED] (see study reference manual for guidance on providing documentation of SAE).

The Investigator is responsible for expedited reporting of all Serious Adverse Events immediately to BPL and / or the designated CRO except for those that the protocol or Investigator's Brochure identifies as not requiring immediate reporting. This reporting requirement covers any serious adverse events that develop at any point between the date when a subject provides informed consent and up to 28 days after the last administration of the investigational medicinal product (HRIG or rabies vaccine). The investigator is also responsible for reporting to BPL and / or the designated CRO any serious adverse events with an onset date more than 28 days after the last administration of the product if he/she judges the serious adverse event to be possibly, probably or very likely/certainly related to the product.

The immediate report should contain the following as a minimum:

- a suspected investigational medicinal product
- study subject number
- details of the serious adverse event
- classification of SAE
- causality of SAE (if available)

The immediate SAE form should be followed by a detailed, complete SAE form as soon as possible. The immediate report and follow-up reports shall identify subjects by unique code numbers assigned to the latter.

Adverse events and/or laboratory abnormalities identified in the protocol as critical to the evaluation of safety must be reported to BPL and / or the designated CRO by the Investigator according to the reporting requirements within the time periods specified in this protocol.

The investigator must not wait to receive additional information to document fully the event before notification of a SAE, though additional information may be requested. Where applicable, information from relevant laboratory results, hospital case records and autopsy reports should be obtained.

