5. The geometric mean titers (GMTs) for anti-rabies antibody titer at Visit 6-9 will be compared between treatment groups. Descriptive statistics and visual inspections will be reported as appropriate. No formal hypotheses testing will be performed.

g. EXPLORATORY PK ANALYSES

The following PK parameters for anti-rabies antibody concentrations will be summarized for both treatment groups:

- C_{\max} [IU/mL]
- T_{\max} [day]
- area under the concentration vs time curve to the last measurable concentration (AUC_{0-t}) [day*IU/mL]
- apparent terminal rate constant (λ_z) [day⁻¹]
- AUC_{0-7d} [day*IU/mL]
- area under the concentration vs time curve to infinity ($AUC_{0-\infty}$), if appropriate

- $C_{\max}/AUC_{0-\infty}$ [or C_{\max}/AUC_{0-t} if $AUC_{0-\infty}$ cannot be estimated]
- half-life ($t_{1/2}$), if appropriate

Non-compartmental PK methods will be utilized to calculate the subject level PK parameters. C_{\max} , AUC_{0-t} , AUC_{0-7d} , $AUC_{0-\infty}$, apparent terminal rate constant (λ_z), and $t_{1/2}$ will be dose normalized by dividing the raw PK parameters by the actual dose the subject received. A t-test will compare the PK and dose-normalized PK parameters between treatment groups. Log-transformations will be performed as necessary during statistical analysis when appropriate.

h. ADVERSE EVENT REPORTING

Adverse events (AEs) will be reported by the MedDRA system organ class and preferred term. Only treatment emergent AEs (i.e. beginning after dosing with BPL HRIG / vaccine or comparator HRIG / vaccine) will be included in the summary tables. All AEs will be included in the data listings.

Treatment-related AEs will be defined as events recorded as having a possible, probable or very likely/certain causality to treatment. AEs leading to withdrawal will be defined as events where the subject's participation in the study was discontinued as a result of the AE.

AEs will be summarized descriptively for all subjects and by treatment group. The denominator used for the calculation of percentages will be the number of subjects in the safety population per treatment group. For all AE summaries described below, counting will be performed by subject and event. For counts by subject, subjects experiencing the same event more than once will have that event counted only once within each system organ class and once within each preferred term.

The following summaries of treatment-emergent AEs will be provided:

SUMMARY OF AEs

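### The SAP's unrestricted no-imputation rule leaves AEs with blank causality, blank severity or an onset ambiguous around Day 0 without a conservative convention, and so permits some undercounting

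*SAP*

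**What the plan says.** SAP 8.K (Missing Values): "No missing value imputation methods will be applied, e.g. the analyses are based on a valid case basis". The section names no type of variable. It comes after adverse-event reporting (8.h) and before the other safety sections.

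SAP 8.h fixes the AE tables by three statements:

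- Relatedness: "Treatment-related AEs will be defined as events recorded as having a possible, probable or very likely/certain causality to treatment".
- Entry to the summary tables: "Only treatment emergent AEs (i.e. beginning after dosing with BPL HRIG / vaccine or comparator HRIG / vaccine". Protocol 10.6.1 words the same filter by date: "defined as those events with onset date from dosing with" study product.
- Denominator: "The denominator used for the calculation of percentages will be the number of subjects in the safety population per treatment group".

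The causality table in 8.h has five levels and the severity table three. Neither has a level for missing. 8.h also says "All AEs will be included in the data listings".

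On collection, Protocol Appendix A 3.1 asks the investigator to judge causality for each medication and to record start date and time and severity. Appendix A 3.4 asks for a severity grade for each AE and SAE. Appendix A 5 lists "causality of SAE (if available" among the minimum contents of the immediate SAE report.

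Neither document says how to classify an AE whose causality or severity is blank, or whose onset date is missing or partial.

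**The concern.** Leaving a missing value out is neutral for many summaries, but not for a count of related events over a fixed denominator. There, an unclassified event has the same effect on the table as an unrelated one. The usual safeguard is to classify incomplete AE records against the product. Read literally, 8.K rules that safeguard out, and 8.h puts nothing in its place.

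Safety is the fourth study objective. Protocol 10.6 makes the comparison purely descriptive, so the tables are the safety evidence. Protocol 2.5 states that BPL HRIG has had no earlier clinical trial, and Protocol 2.9 says the data are meant for a US licence application. For the primary endpoint the SAP adds best-case and worst-case analyses of non-compliers; for incomplete safety records it offers nothing comparable. If the choice is left to programming, or made after unblinding, it could look driven by the data.

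**Working it through.** The plan gives no figure for missing AE causality, severity or onset, so there is nothing to reproduce. The check reads the texts together and then shows a range under stated assumptions.

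**1. Causality.** By 8.h an event is related only if the recorded entry says possible or higher. A blank entry fails that test. The denominator is the safety population, not the subjects with complete records. The numerator can therefore lose the event while the denominator keeps the subject. The mechanism is the 8.h definition; 8.K prevents the repair. A subject with another AE recorded as related still counts in the overall related-AE row, so a blank record does not always cost a subject.

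**2. Onset.** AEs are collected from consent (Protocol 8.2.1), which may be up to 28 days before Day 0, so the treatment-emergent filter does exclude some events. A month-only date can fit both sides of dosing. On Day 0 itself, the data list in Appendix A 2.3 asks only for the date, while Appendix A 3.1 asks for date and time. A Day 0 event without a time meets the protocol's date-based wording more easily than the SAP's requirement that it begin after dosing. Where neither the known date parts nor the collection visit settles the order, no text places the event in the tables. If it truly began after dosing, leaving it out is an undercount; if before, leaving it out is right.

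**3. Severity.** The maximum-severity table has three ordered levels, so a blank has no cell.

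**4. What does not change.** Counts of all treatment-emergent AEs, SAEs, withdrawals and deaths do not use causality. All AEs are listed.

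**5. Illustrative size for the related-AE row.**

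Inputs: n = 81 per arm (SAP section 4, assuming every randomized subject is dosed). True related-AE incidence R = 20% to 60%, and share m = 1% to 10% of those subjects with no countable causality entry. R and m are assumptions; the documents give neither.

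- Weight of one subject: 1/81 = 1.23 percentage points.
- Reported incidence = R × (1 − m); shortfall = R × m; subjects lost = 81 × R × m.

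| R | m | Reported | Shortfall (points) | Subjects lost of 81 |
|---|---|---|---|---|
| 20% | 1% | 19.8% | 0.2 | 0.16 |
| 40% | 5% | 38.0% | 2.0 | 1.62 |
| 60% | 10% | 54.0% | 6.0 | 4.86 |

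With the same m in both arms, the reported difference is (R_BPL − R_comparator) × (1 − m): it shrinks in proportion, and is zero if the true rates are equal.

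**The case against.** The strongest reply is that the records in question should be rare. Causality, severity and onset are required for every AE, monitors verify source data, and the eCRF carries a query trail. This stands, and it is the main reason to expect a small effect.

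A reader might infer several stronger points that the documents do not support:

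- *That 8.K declares such events unrelated.* It does not. Under a valid-case reading they are unclassified; the loss from the related row follows from the 8.h definition.
- *That any AE with an incomplete date drops out of every table.* No text says so. Each later visit asks about events new or changed since the last one, and the flow chart separates pre-dose, dosing and 30 minutes post-dose on Day 0. An event first arising between Day 49 and Day 140 is plainly post-dose without imputation. Only dates that fit both sides of Day 0 are at issue.
- *That the protocol expects SAE causality to stay missing.* The qualifier in Appendix A 5 applies to the immediate notification. A complete form must follow, and Appendix A 5.1 lists causal relationship among its required contents.
- *That a related SAE could vanish.* With blank causality it would be absent from the related row only; it stays in the SAE row and the listing.

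Against all this, required collection does not tell the programmer what to do with a field that is still blank at lock. That gap remains.

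**Conclusion.** The point holds in a limited form. Read with 8.h, the unrestricted rule in 8.K bars conservative handling of AEs with blank causality and gives no place to those with blank severity or an onset ambiguous around Day 0. For the related count, any error runs toward understating risk. It is not shown that the safety tables as a whole are biased low, nor that the comparison between arms is distorted.

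The size cannot be derived from the documents. The illustrative shortfall of 0.2 to 6.0 percentage points per arm rests wholly on assumed incidence and missingness; given the collection requirements, the true figure is probably toward the low end. Sample size, power and the primary analysis are untouched. This is a cheap improvement to make before unblinding, not a fault that threatens the trial's conclusions.

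**What to change.** Add an AE exception to SAP 8.K and leave the rule as it stands for efficacy, PK, laboratory and vital-sign variables, which would otherwise have no missing-data rule. In 8.h, state that:

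- an AE with missing causality is counted as related;
- an AE with a missing or partial onset is treatment-emergent unless the known date parts or the collection visit show that it began before dosing;
- missing severity is shown in a separate row for missing, with a worst-case count as a sensitivity display if wanted. Blanks should not be forced into the top grade: on the Appendix A 3.4 scale that would report them as potentially life-threatening or fatal.

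Footnote each table with the number of records handled this way.

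The cost is one SAP paragraph and minor programming. AE rates may look slightly less favourable.
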